1.5 Statistical considerations

The principal hypothesis to be tested in this work is that wearing times for young and old wearers will be the same. Wearing time data are likely to be normally distributed and so the impact of age will be explored using linear regression models or other parametric methods.

Deviations from this plan will be discussed in the final report. Deviations may be necessary due to differences between the actual data distribution compared with the anticipated data distribution.

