1.3 Study objectives

This study aims to compare the wearing patterns of spectacles for myopia control across different ages, different levels of myopia and between males and females.

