1.5.2 Power analysis

Power analysis was conducted based on information from a previous study [REDACTED]

[REDACTED], assuming (a) that males vs. females are compared and (b) younger vs. older subjects are compared. For sex, power analysis based on previous data in spectacle wearers shows that for a two-sided two-sample t-test with an alpha of 0.05, assuming standard deviations of 0.95 for females and 2.61 for males, a sample size of 17 subjects in each group is required to detect a 2-hour difference in daily wearing time between groups with 80% power.

For age, power analysis on the same basis, assuming standard deviations of 3.31 for older subjects (> 10 years) and 0.68 for younger subjects (< 10 years), a sample size of 25 subjects in each group is required to detect a 2-hour difference in daily wearing time between groups with 80% power.

Given this, 60 subjects will be recruited to comprise approximately 50% males and 50% females, and with subjects recruited across the full age range. Subjects will be recruited into the following prescription range 'bins' (mean sphere) in approximately equal numbers; 1) plano to -1.50DS, 2) -1.75 to -3.75DS and 3) -4.00DS and above.

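### Does stating the principal hypothesis as equal wearing times commit the study to showing sameness with a test that can only detect a difference?

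*Combined protocol and SAP*

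**What the plan says.** Section 1.5 (Statistical considerations) gives the inferential target in one sentence: "The principal hypothesis to be tested in this work is that wearing times for young and old wearers will be the same". It does not use the word null and states no alternative. On method, it says that "the impact of age will be explored using linear regression models or other parametric methods".

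Section 1.3 (Study objectives) sets the purpose: "This study aims to compare the wearing patterns of spectacles for myopia control across different ages, different levels of myopia and between males and females".

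Section 1.5.2 (Power analysis) gives the test, first for sex: "for a two-sided two-sample t-test with an alpha of 0.05". It then turns to age: "For age, power analysis on the same basis", with standard deviations of 3.31 h for older and 0.68 h for younger subjects. The result is that "a sample size of 25 subjects in each group is required to detect a 2-hour difference in daily wearing time between groups with 80% power". Total recruitment is 60. The sexes are to be roughly balanced; for age the plan asks only for recruitment across the range.

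The visible text gives no equivalence margin, promises no confidence interval and does not say how a non-significant age result will be read.

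**The concern.** A significance test can reject equality but cannot establish it. If equality is the proposition the study hopes to confirm, a p-value above 0.05 leaves it standing, and a report could conclude that younger and older children wear their spectacles for the same time when the data still allow a sizeable gap. This is the plan's principal hypothesis, so the headline conclusion is at stake.

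The risk is not trivial at this sample size. Under the plan's own assumptions, a true difference well short of 2 h would often be non-significant. The plan also names a 2-hour difference for power but does not refer to it when describing how the result will be interpreted.

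**Working it through.** **Inputs (section 1.5.2).** SDs 3.31 h (older) and 0.68 h (younger); difference 2 h; two-sided alpha 0.05; 80% power; 25 per group; 60 in total. The 30/30 age split is an assumption, because the plan fixes no split by age.

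**1. Reproduce the plan's figure.** Sum of variances: 3.31² + 0.68² = 10.9561 + 0.4624 = 11.4185.

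- Normal approximation: n = (1.960 + 0.842)² × 11.4185 / 2² ≈ 22.4, so 23 per group.
- Welch t-test at n = 25: SE = √(11.4185/25) = 0.676 h. Degrees of freedom = (n − 1) × 11.4185² / (10.9561² + 0.4624²) = 24 × 1.084 = 26.0. Non-centrality = 2/0.676 = 2.96. Power = 81.3%. The smallest n reaching 80% is 25, which is the plan's figure.

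The sex figure of 17 per group reproduces in the same way (power 80.7%). Both are calculations for detecting a difference.

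**2. What a non-significant result would leave open.** 95% half-width = t(0.975, df) × SE:

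| Per group | SE (h) | df | t | Half-width (h) |
|---|---|---|---|---|
| 25 | 0.676 | 26.0 | 2.055 | 1.39 |
| 30 | 0.617 | 31.4 | 2.038 | 1.26 |

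For example, an observed difference of 1.2 h at 30/30 has a 95% interval from 1.2 − 1.26 = −0.06 h to 1.2 + 1.26 = 2.46 h. That is non-significant, yet it does not exclude 2 h.

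Chance of a non-significant result, by true difference:

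| True difference | 25 per group | 30 per group |
|---|---|---|
| 1 h | 70% | 65% |
| 1.5 h | 43% | 35% |
| 2 h | 19% | 12% |

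So non-significance would be weak evidence of sameness. The remaining question is whether the plan says it will be used that way.

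**3. Set the sections side by side.** If the sentence in 1.5 is a null hypothesis, every other element fits: an aim to compare (1.3), an effect of age to be explored (1.5), a two-sided test whose implied alternative is a difference in either direction (1.5.2), and a sample size for detecting 2 h (reproduced above). If it is an equivalence claim, none of them fits: there is no margin, no interval rule and no matching sample size. The mismatch arises only under the second reading, which no section supports.

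**4. Would a formal equivalence rule be a gain?** The documents give no margin, so those below are assumptions. Power of two one-sided 5% Welch tests when the true difference is zero (simulation, 200,000 draws), and the n per group needed for 80%:

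| Margin | 25 per group | 30 per group | n for 80% |
|---|---|---|---|
| ±2 h | 78% | 87% | 26 |
| ±1.5 h | 40% | 54% | 45 |
| ±1 h | 2% | 5% | 100 |

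Only ±2 h is workable at the planned size, and in 1.5.2 the figure of 2 h is a detectable difference, not a margin. Using it as one has an awkward result. At 30/30 the 90% half-width is 1.05 h, so an observed difference of 0.9 h has an upper 90% limit of 1.95 h and would be declared the same. Its upper 95% limit is 0.9 + 1.26 = 2.16 h, so that interval still does not exclude 2 h.

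**The case for a change.** The best case for a change is that section 1.5 is the only place where the principal inference is stated, and it neither labels the null nor says what a non-significant result means. Whatever the authors intended, nothing written stops a report from treating p > 0.05 as confirmation. Section 2 of the working shows that this outcome is likely for true differences of 1 h or so. A clarification would cost a couple of sentences and no subjects, and writing it before analysis would prevent a choice of interpretation after the data are seen.

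The facts in that case stand: the label, the interval and the reading rule are all absent. The inference drawn from them is weaker. That non-significance does not prove equality is a general caution for any test of difference, and plans for small studies often leave it unsaid. The harm requires the analyst to make an elementary error that the plan does not direct. A linear regression, which 1.5 names, gives an estimate and standard error as ordinary output, so the interval that guards against the error is available without an instruction. A more substantive remedy, a ±2 h equivalence rule, would open a formal route to a claim of sameness that the plan does not make, with a margin the documents do not justify.

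**Conclusion.** The concern does not hold as a defect. Section 1.5 states a null hypothesis in ordinary terms without naming it as such. Followed as written, the plan gives a valid two-sided test of an age difference, sized consistently at 25 per group (81.3% power for 2 h). The gap is one of missing detail that analysts fill sensibly by reporting the age effect with its 95% interval and not reading non-significance as equality.

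The caution about interpretation is correct: the expected 95% half-width is about 1.26 to 1.39 h, so a non-significant result could coexist with a difference of 2 h or more. These figures rest on the plan's SDs, on group sizes of 25 or 30 (an even age split is assumed) and on a two-group Welch comparison. A regression on age as a continuous variable would have different precision. None of this alters the design, the test or the sample size. Labelling the null would be a matter of tidiness, and adding an equivalence margin would be a debatable trade-off, not a correction.

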2.1.3 Inclusion criteria

Subjects will only be eligible for the study if:

1. They are aged between six and 15 years old.
2. Their parent or guardian understands the rights of the subject and are willing to sign a statement of informed consent.
3. They understand the study at a level appropriate for their age and are willing to sign a statement of assent.
4. They and their parents or guardians are willing and able to follow the protocol.
5. They currently use spectacle lenses for myopia control and have done so for at least three months.
6. They agree not to participate in other clinical research for the duration of this study.

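### Section 1.5 should name one primary age analysis with unequal-variance inference, because section 1.5.2 assumes SDs of 3.31 h and 0.68 h for that comparison (minor)

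*Combined protocol and SAP*

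**What the plan says.** All references are to the combined protocol and SAP.

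- **Objective (1.3).** The study aims to "compare the wearing patterns of spectacles for myopia control across different ages", as well as by level of myopia and by sex.
- **Principal hypothesis (1.5).** "The principal hypothesis to be tested in this work is that wearing times for young and old wearers will be the same".
- **Method (1.5).** The data are "likely to be normally distributed and so the impact of age will be explored using linear regression models or other parametric methods". No variance method is named.
- **Departures (1.5).** "Deviations may be necessary due to differences between the actual data distribution compared with the anticipated data distribution"; these are to be discussed in the final report.
- **Sizing (1.5.2).** The calculation for sex is for a "two-sided two-sample t-test with an alpha of 0.05", and age is handled on the same footing. The age SDs are "3.31 for older subjects (> 10 years) and 0.68 for younger subjects (< 10 years"). The result is 25 per group for a 2-hour difference with 80% power. The section does not say whether variances are pooled.
- **Recruitment (1.5.2, 2.1, 2.1.3).** Sixty children are to be recruited, with targets for sex and for prescription bins. For age, the plan says only "with subjects recruited across the full age range". The inclusion criterion is "They are aged between six and 15 years old".

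**The concern.** Expected normality does not by itself support a common variance. The plan assumes an SD ratio of 3.31/0.68 = 4.9 (a variance ratio of about 23.7) between the two groups in its principal comparison, but the analysis section does not carry this forward. Default regression standard errors and the pooled t-test both assume one variance.

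When group sizes are equal, that assumption does little harm. When they are unequal, the standard error is wrong in a direction that depends on which group is larger. The age split is left to recruitment, so the true error rate of the principal test would depend on which ages happened to enrol.

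The clause on departures does not settle this. It covers data that differ from the anticipated distribution, and here the unequal spread is itself what is anticipated.

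**Working it through.** **Inputs.** SDs 3.31 (older) and 0.68 (younger), difference 2 h, two-sided alpha 0.05, 25 per group and N = 60, all from 1.5.2. The SDs are taken to be in hours per day, to match the 2-hour difference. Ages 6 to 15 come from 2.1.3. The age splits below are assumptions, shown as a range.

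**Step 1: reproduce the plan's figure.** With 25 per group, SE = √(3.31²/25 + 0.68²/25) = 0.676 h. The Welch–Satterthwaite degrees of freedom are about 26, and noncentral-t power is 81.3%. At 24 per group power is 79.6%, so Welch gives exactly 25. Pooled degrees of freedom give 24, and the normal approximation gives 23. The stated sample size is sound.

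**Step 2: plausible splits of 60 (older/younger).** An even age spread gives:
- exact age from 6 to just under 16: 6/10 older, 36/24;
- exact age from 6 to 15.0: 5/9 older, about 33/27;
- completed years, with age 10 counted as younger: 5/10 older, 30/30.

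**Step 3: why the pooled test drifts.** True SE = √(3.31²/n₁ + 0.68²/n₂). The pooled test instead uses about √[s²(1/n₁ + 1/n₂)], where s² = [(n₁−1)·3.31² + (n₂−1)·0.68²]/58.

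| Older/younger | Pooled SE (h) | True SE (h) | Ratio |
|---|---|---|---|
| 30/30 | 0.617 | 0.617 | 1.00 |
| 33/27 | 0.649 | 0.591 | 1.10 |
| 36/24 | 0.687 | 0.569 | 1.21 |
| 25/35 | 0.574 | 0.672 | 0.85 |

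A ratio above 1 is conservative, and a ratio below 1 is anti-conservative.

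**Step 4: error and power by simulation.** Normal data, at least 100,000 runs per cell. Independent runs agree to about 0.2 points.

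| Older/younger | Type I, pooled | Type I, Welch | Power for 2 h, pooled | Power for 2 h, Welch |
|---|---|---|---|---|
| 30/30 | 5.4% | about 5% | about 89% | about 88% |
| 33/27 | 3.5% | about 5% | 87.8% | 90.9% |
| 36/24 | 2.1% | about 5% | 85.9% | 93.0% |
| 27/33 | about 7.7% | about 5% | – | – |
| 25/35 | 9.8% | about 5% | not comparable | about 82% |

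The power lost by pooling is 90.9 − 87.8 = 3.1 points at 33/27 and 93.0 − 85.9 = 7.1 points at 36/24. At 25/35 the pooled test's apparent power comes from its inflated error rate, so it is not compared. That split still meets the planned 25 per group.

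**Step 5: regression on age.** Assume the SD steps from 0.68 h to 3.31 h at age 10. Default standard errors give a type I error of about 3.7% with ages uniform over 6 to 16, and about 10% at 25/35. HC3 standard errors give about 5 to 6% in both cases.

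**Step 6: sensitivity to the SD ratio.** If the ratio is 2 rather than 4.9, the pooled test gives 7.8% at 25/35 and 2.8% at 36/24. The direction is the same and the effect is smaller.

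**The case against.** The strongest reply is that nothing in section 1.5 is wrong. Its wording allows Welch's test or robust standard errors, and the age sample size fits a Welch calculation exactly, so the planners may already have had unequal variances in mind. This stands in part. The documents do not commit to a common-variance analysis, and a reader who inferred that they do would go too far. Equally, a sizing calculation does not fix the analysis, and pooled degrees of freedom give 24, too close to 25 to settle which method was used.

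A second reply is that the likely effect is benign. This stands. Under an even age spread the pooled test is nominal to conservative, and its power stays above the planned 80%. A reader might infer from the 9.8% that false positives on the principal test will probably double. The documents do not support that, because no section predicts a minority of older children. If children enrol independently (an assumption), the chance of 25 or fewer older children among 60 is 12% when the two groups are equally likely, 2% when 5/9 are older and 0.3% when 60% are older.

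Three further readings should be resisted:
- **Larger regression errors.** If the SD is assumed to rise linearly with age, default regression gives 9.0% with ages uniform over 6 to 16 and 17.5% at 25/35. That curve has no basis in the documents, so these figures carry no weight here.
- **Age 10.** Neither age group in 1.5.2 includes age 10, and the plan does not say whether age is exact or in completed years. This is a matter of definition and does not make the concern more serious.
- **Choice after seeing the data.** Naming a type of standard error would not by itself prevent this. Only naming a single primary age analysis does, and the report's discussion of departures gives only partial cover.

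**Conclusion.** The point holds as a minor one. The plan anticipates a nearly fivefold SD difference in its principal comparison, justifies its method by normality alone, and fixes neither the variance method nor the age split.

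If default common-variance inference were used, the likely result under an even age spread is a type I error between 2.1% and 5.4%, with up to about 7 points of power given away. The less likely result, with older children in the minority, is an error of about 8 to 10% at 27/33 to 25/35.

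These figures assume normal data, the plan's SDs, all 60 children analysed and the stated splits. The regression figures also assume an SD step at age 10. The source of the SDs is redacted, so their precision cannot be judged. The sample size is not in question.

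**What to change.** In section 1.5, name one primary age analysis in advance and state its unequal-variance inference. It should be one of these, not a choice left open:
- regression on age with HC3 standard errors, which keeps the method the plan names first; or
- Welch's t-test of older against younger children, which matches the sizing. In that case, also state how age is counted and which group takes age 10.

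**Cost.** One or two sentences and no extra data. If the variances prove equal (SD 2.39 h, the root mean square of the two assumed SDs), Welch loses about 0.2 points of power (87.6% against 87.8% at 36/24). HC3 regression loses about 1.6 points (76.4% against 78.0%, for an assumed slope of 0.3 h per year).

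**Limit.** If few older children enrol, power is lower but honest: about 82% at 25/35 with Welch. The change corrects the error rate but cannot recover power lost to an unfavourable split.

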1.4 Study design

This will be an unmasked multi-centre study which is controlled by cross-comparison. The wearing patterns of up to 60 established spectacle wearers will be evaluated via the use of temperature sensors fitted to the side of their spectacles. [REDACTED]

[REDACTED]

[REDACTED]. Subjects will wear the sensor for approximately one month. The data from the final week of this period will be used for analysis, in an attempt to minimise 'unusual' wear patterns which may occur early in the study as the subject adapts to being on a clinical study.

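### Section 1.5 fixes no single principal analysis of age and lets it change on the observed distribution, so the 5% level assumed in 1.5.2 is not secured

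*Combined protocol and SAP*

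**What the plan says.** All references are to the combined protocol and SAP.

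- **Hypothesis (1.5):** "The principal hypothesis to be tested in this work is that wearing times for young and old wearers will be the same".
- **Method (1.5):** "Wearing time data are likely to be normally distributed and so the impact of age will be explored using linear regression models or other parametric" (cut before the last word of the sentence). No single model, age coding or variance assumption is chosen.
- **Change of method (1.5):** "Deviations from this plan will be discussed in the final report", followed by "Deviations may be necessary due to differences between the actual data distribution compared with the anticipated data distribution". The section does not say how the distribution is to be judged, what would replace the planned method, when the decision is made, or whether it is made without sight of age.
- **Sample size (1.5.2):** the calculations are "for a two-sided two-sample t-test with an alpha of 0.05". For age the calculation is made "assuming standard deviations of 3.31 for older subjects (> 10 years) and 0.68 for younger subjects (< 10 years"), giving 25 per group for a 2-hour difference in daily wearing time at 80% power. The total is 60, recruited across the age range with no quota per age group.
- **Design (1.4):** "This will be an unmasked multi-centre study which is controlled by cross-comparison".

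Sections 1.5.1 and 2.1.1 deal with missing data, spurious data and exclusions. They do not limit the choice of test.

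**The concern.** A 5% error rate belongs to a procedure, and section 1.5 does not define one. Two choices are left open: which parametric method is used, and whether it is replaced once the distribution is known. Disclosing a change lets a reader see it, but does not bring the error rate back to 5%.

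The plan's own figures make a change foreseeable. Ordinary linear regression assumes one residual variance, whereas 1.5.2 assumes SDs whose variances differ about 24-fold. Residuals pooled from two such groups look non-normal even if each group is normal.

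At stake is the principal conclusion. A rank test is a common replacement. It does not estimate the 2-hour mean difference the study is sized for, and Mann-Whitney can reject because spreads differ when means do not.

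**Working it through.** **1. Reproduce the plan's figure.** Inputs from 1.5.2: SDs 3.31 and 0.68, difference 2 hours, two-sided alpha 0.05, n = 25 per group.

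- Variances: 3.31² = 10.956 and 0.68² = 0.462; ratio 10.956 / 0.462 = 23.7.
- Standard error: √[(10.956 + 0.462) / 25] = √0.4567 = 0.676.
- Noncentrality: 2 / 0.676 = 2.96.
- Satterthwaite df: 24 × (10.956 + 0.462)² / (10.956² + 0.462²) = 24 × 130.38 / 120.25 = 26.0.
- Power from the noncentral t: 81.3%. The smallest n reaching 80% is 25, as the plan states.

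With pooled df (2n − 2) the smallest n is 24, so the stated 25 matches the Welch form. The same Welch method gives the plan's 17 per group for sex (power 80.7%).

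**2. How often a check would fail.** Simulation with equal means, normal data within each age group, the plan's SDs, ages uniform within groups, 10,000 trials per scenario. At 30 v 30:

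- equal-variance tests: about 100%;
- Breusch-Pagan on regression residuals: 94%;
- Shapiro-Wilk on regression residuals: 92% (85% at 25/25, 73% at 36 older/24 younger, 98% at 24/36);
- Shapiro-Wilk within each age group, either failing: 10%, which is the false-alarm rate of two tests.

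**3. False-positive rate of each procedure (%).** Monte Carlo standard error is about 0.2 to 0.4 points. Splits are older/younger; 1.5.2 does not fix the split, so four are shown.

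| Procedure | 30/30 | 25/25 | 36/24 | 24/36 |
|---|---|---|---|---|
| Fixed Welch t | 5.2 | 5.2 | 5.1 | 4.8 |
| Fixed regression on age, HC3 | 5.3 | 5.1 | 5.5 | 5.4 |
| Fixed pooled t | 5.6 | 5.6 | 2.0 | 10.9 |
| Fixed ordinary regression on age | 6.0 | 5.9 | 3.7 | 10.8 |
| Fixed Mann-Whitney | 7.8 | 7.7 | 5.0 | 10.7 |
| Pooled t, to Welch if variance test fails | 5.2 | 5.2 | 5.1 | 4.8 |
| Regression, to HC3 if Breusch-Pagan fails | 4.9 | 4.5 | 4.7 | 5.3 |
| Regression, to Spearman if residual normality fails | 7.6 | 7.9 | 6.4 | 8.6 |
| Pooled t, to Mann-Whitney if residual normality fails | 8.1 | 8.3 | 5.0 | 10.9 |
| Better of regression and pooled t | 8.6 | 8.8 | 4.9 | 15.2 |
| Better of Welch and Mann-Whitney | 9.3 | 9.2 | 7.3 | 11.6 |
| Best of regression, Spearman, Welch, Mann-Whitney | 13.4 | 13.4 | 10.9 | 17.8 |

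**4. Control run.** With a common SD of 2.39 (√[(10.956 + 0.462) / 2]) at 30/30, the two rank switches give 5.0% and 5.2%, the better of Welch and Mann-Whitney 6.1%, and the better of regression and pooled t 7.4%.

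**5. Reading.** The two switches to methods that allow unequal variance stay at 4.5% to 5.3% on every split. The two rank switches give about 8% at equal group sizes and range from 5.0% to 10.9% over the splits. Choosing between regression and pooled t needs no deviation from the plan at all, and gives 8.6% at 30/30.

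**The case against.** **The trigger may not fire.** A reader might infer that a change of method is almost certain. The documents do not support that. The clause refers to a departure from the anticipated distribution, and SDs of 3.31 and 0.68 are part of what 1.5.2 anticipates. The 92% belongs to a check the plan does not name. Within-group checks fail in about 10% of trials. In a separate run of 4,000 trials, residuals scaled by their own group's SD failed in 4.5%, and switching on that check gave 5.4% error. This stands. What remains is that unequal SDs conflict with ordinary regression, and the plan does not say which check counts.

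**A switch need not inflate the error.** A reader might also infer that the error rate is definitely not 5%. Moving to Welch or HC3 keeps it there, and no rank test is named anywhere. A fixed Mann-Whitney already gives 7.8%, so most of the excess in the rank switch comes from unequal spread rather than from switching. This stands too, and limits the claim to an undefined rate that may exceed 5%.

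**Unmasked describes the design.** Section 1.4 does not say that analysts choose the test with age-group results in view. That is an inference, although the observed distribution can only be known from collected data and nothing requires the choice to be made blind to age.

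**Larger error rates can be constructed.** A skewed older group with a ceiling on daily hours makes a rank test reject far more often at equal means. Such ceilings have no source in the documents. In those cases wearing times really do differ between age groups, and the hypothesis in 1.5 is not restricted to means, so those rejections are not clean false positives.

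**Disclosure is promised and the study is small and exploratory in tone.** Disclosure would expose a displaced result. It does not set the error rate of a hypothesis the plan itself calls principal.

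**Conclusion.** The point holds. Section 1.5 neither fixes one principal analysis of age nor bounds how it may change, so the two-sided 5% in 1.5.2 is not attached to any defined procedure. At the plan's SDs and 30 v 30, plausible routes run from about 5% (Welch or HC3), through about 8% (rank test after a residual-normality check) and 9% (better of Welch and Mann-Whitney), to 13% (free choice among four tests).

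These figures assume equal means, normal data within groups and uniform ages within groups. They also depend on the age split: with more older than younger subjects the rank switch is close to nominal, and with fewer it is worse. The plan is not shown to exceed 5%; it is shown not to prevent it. This is a cheap improvement to make before data are seen, not a flaw in the sample size, which reproduces exactly.

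**What to change.** In 1.5, replace both the open choice of parametric method and the sentence permitting distribution-driven deviations with:

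> The principal result is the difference in mean daily wearing hours between older and younger subjects with its 95% CI from a Welch (unequal-variance) two-sample t-test, and it is reported as principal whatever the observed distribution. Linear regression on age with HC3 standard errors, a bootstrap CI and a rank-based test are sensitivity analyses and cannot replace it.

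Both parts must go: removing only the deviation sentence leaves the choice between regression and other parametric methods open. The text should also say which group a child aged exactly 10 joins, since the strict inequalities in 1.5.2 place that child in neither. The commitment to discuss deviations in the report can stay.

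**Cost.** Two sentences and a few sensitivity lines in the report; no extra subjects or procedures. Welch matches the calculation that gives 25 per group (81.3% power; 88.1% at 30 per group). The downside is some loss of efficiency, and slightly more than 5% error, if wearing times are heavily skewed.
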